### 12.2.4 Antitumor Activity (Part 1 and 3)

No formal statistical analysis of efficacy was performed for Part 1 and Part 3. For patients with measurable disease, response to treatment per RECIST v1.1. was reported via descriptive statistics by dose level in patient listings.

## 12.3 Exploratory Efficacy Analyses

### 12.3.1 To explore the association between genomic alterations identified in tumor tissue and clinical outcome (Part 1, 2, and 3)

No formal statistical analysis of efficacy was performed for Part 1 and Part 3, thus genomic data and tumor response data will be presented in patient listings.

For Part 2A and Part 2B, the proportion of patients with the best confirmed response by RECIST Version 1.1 of CR or PR and the proportion of patients with best confirmed response by RECIST Version 1.1 or response according to the GCIG CA-125 criteria were summarized by BRCA

mutation type (BRCA1 or BRCA2). The ORR will be summarized with frequencies and proportion together with 95% Confidence Interval (CI) of the proportion using Clopper-Pearson methodology for each subgroup.

### ***12.3.2 Time to first Response per RECIST version 1.1 (Part 2A and Part 2B).***

The frequency and percentages of patients with a response (CR or PR) will be summarized by the first occurrence using the following time points;  $\leq 8$  weeks (Cycle 2),  $\leq 14$  weeks (Cycle 4),  $\leq 20$  weeks (Cycle 6),  $\leq 30$  weeks (Cycle 8), and  $> 30$  weeks.

### ***12.3.3 Change from Baseline in Sum of the Longest Diameters (SD) of Target Lesion (Part 2A and Part 2B)***

The largest percent decrease from baseline in the sum of the diameters (SD) of target lesions as identified by RECIST v1.1 will be displayed graphically using a waterfall plot. This will be based on the investigator assessed tumor responses and only presented for patients with measurable disease at baseline and one valid post-baseline evaluation of the target lesions.

## **13 STATISTICAL/ANALYTICAL ISSUES**

### **13.1 Handling of Dropouts or Missing Data**

All data will be used to their maximum possible extent but without any imputations for missing data. All time to event endpoints are censored and the rules for deriving the censoring value is described in more detail under each one of the time to event endpoints.

### **13.2 Pooling of Centers in Multi-Center Studies**

Data from all centers will be pooled.

### **13.3 Multiple Comparison/Multiplicity**

No adjustments for multiple comparisons will be made.

## 14 SAFETY ANALYSIS

The safety analyses will be performed using the safety population for each part of the study separately.

### 14.1 Adverse Events

Adverse events will be classified using the Medical Dictionary for Drug Regulatory Activities (MedDRA) classification system with version 19.1 or higher. The severity of the toxicities will be graded according to the NCI CTCAE v.4.03 or higher. Treatment-emergent adverse events (TEAEs) are defined as AEs with onset date on or after the date of first dose of study medication until the date of the last study medication dose plus 28 days. Adverse events will be considered treatment-emergent if all or part of the date of onset of the adverse event is missing and it cannot be determined if the adverse event meets the definition for treatment-emergent.

The number and percentage of patients who experienced TEAEs for each system organ class and preferred term will be presented. Multiple instances of the TEAE in each system organ class and multiple occurrences of the same preferred term are counted only once per patient. The number and percentage of patients with at least one TEAE will also be summarized.

Separate tables will be presented as follows:

- All TEAEs;
- TEAEs by CTCAE grade;
- Grade 3 or greater TEAEs;
- Treatment-related TEAEs;
- Serious TEAEs;
- Serious treatment-related TEAEs;
- TEAEs with an outcome of death;
- TEAEs leading to discontinuation of rucaparib;
- TEAEs resulting in interruption of rucaparib; and
- TEAEs resulting in reduction of rucaparib
- TEAEs resulting in reduction/interruption of rucaparib.
- Time to the first TEAE that results in a reduction, delay, interruption or discontinuation of rucaparib; and
- Time to the first treatment-related TEAE that results in a reduction, delay, interruption or discontinuation of rucaparib.

The incidence of TEAEs will be summarized by relationship to study drug according to the following categories: “treatment-related,” or “not treatment-related”. The category of treatment-related is defined as a relationship of “Possible/Probable”, “Definitely”, or missing. If a patient experiences multiple occurrences of the same AE with different relationship categories, the patient will be counted once as a relationship category of treatment related.

If a patient experiences multiple occurrences of the same AE with different toxicity grades, the patient will be counted once for the maximum (most severe) toxicity grade. AEs with a missing toxicity grade will be presented in the summary table with a toxicity grade of “Missing.” For each toxicity grade, the number and percentage of patients with at least one TEAE of the given grade will be summarized.

The time to the first TEAE and first treatment-related TEAE event that results in a dose reduction, delay, interruption or discontinuation of study drug is defined as 1+ the number of days from the first dose of study drug to the start of the first adverse event. The cumulative incidence is presented in a 1-KM graph and the median time to onset will be calculated together with the 95% Confidence interval.

Dose-limiting toxicities will be presented in a patient listing.

Non-TEAEs will be presented in a patient data listing for the safety population.

MedDRA PTs were combined for the following similar terms:

- Asthenia/Fatigue
- Alanine Aminotransferase (ALT)/ Aspartate Aminotransferase (AST) Increased
- Anaemia and/or Low/Decreased Haemoglobin
- Thrombocytopenia and/or Low/Decreased Platelets
- Neutropenia and/or Low/Decreased Absolute Neutrophil Count (ANC)

In addition, the analysis of combined terms for anemia may be explored as a time to first event analysis as described above.

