As of November 2014, safety data are available for n=163 ovarian cancer patients treated with 600 mg BID rucaparib monotherapy in the ongoing Phase 2 studies, including Part 1 of this trial. Treatment-related adverse events (all grades) reported in $\geq 15\%$ of patients include: gastrointestinal and related events (nausea, vomiting, dysgeusia, diarrhea, abdominal pain, and decreased appetite); anemia; fatigue/asthenia, and headache. Elevations of ALT and/or AST are also commonly observed. The ALT/AST elevations occur early (within first 2-4 weeks of treatment), are generally mild to moderate (Gr 1-2), are not accompanied by any changes in bilirubin levels, and are often transient, and resolve to within normal ranges, or stabilize. No patient has met the laboratory criteria for Hy's Law.²⁴ As has been observed with rucaparib and other PARP inhibitors, myelosuppression may be delayed and observed after a period of continuous dosing. Grade 3/4 adverse events assessed as treatment-related and occurring in $>5\%$ of patients include: anemia/decreased hemoglobin and increased ALT. All treatment-related adverse events have been successfully managed with concomitant medications, and treatment interruption and/or dose reduction. No patient has discontinued rucaparib treatment due to a treatment-related adverse event. A total of five patients have died on study or within 30 days of last dose of rucaparib; all deaths were due to disease progression and were assessed as not related to rucaparib.

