10 ADVERSE EVENT MANAGEMENT

10.1 Definition of an Adverse Event

An AE is defined as any untoward medical occurrence in a patient administered a medicinal product that does not necessarily have a causal relationship with this treatment. An AE can, therefore, be any unfavorable and unintended sign (including an abnormal laboratory finding), symptom, or disease temporally associated with the use of an investigational product, whether or not related to the investigational medicinal product. This includes an exacerbation of pre-existing conditions or events, intercurrent illnesses, drug interaction, or the significant worsening of the indication under investigation that is not recorded elsewhere on the eCRF under specific efficacy assessments. Anticipated fluctuations of pre-existing conditions, including the disease under study, that do not represent a clinically significant exacerbation or worsening are not considered AEs.

For the purposes of this study, disease progression of the patient's tumor with new or worsening symptoms must be documented as an AE. However, disease progression documented solely by radiographic evidence with no new or worsening symptoms will not require reporting as an AE.

It is the responsibility of the investigator to document all AEs that occur during the study. AEs should be elicited by asking the patient a nonleading question (e.g., "Have you experienced any new or changed symptoms since we last asked/since your last visit?"). AEs will be reported on the AE eCRF. Symptoms reported spontaneously by the patient during the physical examination will also be documented on the AE eCRF (not on the physical examination eCRF, which is reserved for physical signs or findings).

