10.4 Events or Outcomes Not Qualifying as Serious Adverse Events

The following are not considered SAEs and therefore are not required to be reported to the Sponsor:

- Pre-planned or elective hospitalization, including social and/or convenience situations (e.g., respite care).
- Hospital visits of less than 24 hours duration (e.g., patient presents to the emergency room, but is not admitted to a ward).
- Overdose of study drug or concomitant medication, unless there is an AE that meets SAE criteria (e.g., hospitalization), as a direct consequence of the overdose. This should be entered as Overdose - followed by the appropriate AE/SAE term.
- Events of disease progression of the patient's underlying cancer as well as events clearly related to disease progression (i.e., signs and symptoms) should not be reported as a SAE unless the outcome is fatal and occurs during the safety reporting period. If the event has a fatal outcome during the safety reporting period, then the event of Progression of Disease must be recorded as an AE/SAE with CTC Grade 5 (fatal outcome) indicated.
- Diagnosis of progression of disease or hospitalization due to signs and symptoms of disease progression alone should not be reported as a SAE.

10.5 Clinical Laboratory Assessments and Other Abnormal Assessments as Adverse Events and Serious Adverse Events

A clinical laboratory abnormality should be documented as an AE if any one of the following conditions is met:

- The abnormality is considered clinically significant by the investigator.

- The abnormality is of a degree that requires active management (change of dose, discontinuation of the drug, more frequent follow-up assessments, further diagnostic investigation, etc.).

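### The SAP's Grade 3+, serious, fatal and discontinuation TEAE totals, and its all-cause time-to-first curve, have no version that sets cancer progression apart

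*SAP*

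**What the plan says.** Protocol section 10.1 divides progression by symptoms. With symptoms, "disease progression of the patient's tumor with new or worsening symptoms must be documented as an AE". Without them, "disease progression documented solely by radiographic evidence with no new or worsening symptoms will not require reporting as an AE".

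Protocol section 10.4 then deals with seriousness. Progression and events clearly related to it "should not be reported as a SAE unless the outcome is fatal and occurs during the safety reporting period". It adds: "Diagnosis of progression of disease or hospitalization due to signs and symptoms of disease progression alone should not be reported as a SAE". For a fatal outcome in that period the instruction is reversed: "then the event of Progression of Disease must be recorded as an AE/SAE with CTC Grade 5 (fatal outcome) indicated". Section 10.2 also makes every death within 28 days of the last dose an SAE.

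SAP section 14.1 counts an AE as treatment-emergent if its onset lies between the first dose and 28 days after the last. It presents TEAEs by system organ class and preferred term, together with the number of patients who have any TEAE. Among its separate tables are Grade 3 or greater, serious, "TEAEs with an outcome of death", and leading to discontinuation. It also plans a time-to-first analysis, shown as a 1-KM curve, of TEAEs that lead to reduction, delay, interruption or discontinuation. Treatment-related versions are listed for all TEAEs, for serious TEAEs and for the time-to-first analysis. A general sentence adds a summary by relationship. The section names five groups of combined preferred terms, and progression is not among them. The table list in protocol section 11.2.8.2 contains no progression rule either.

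SAP section 6 tabulates the primary reason for discontinuation.

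**The concern.** All parts are uncontrolled for safety, and patients are treated until progression unless something else stops them. Progression events will therefore arise inside the TEAE window, and no control arm shows how many would have arisen anyway. Safety and tolerability is a secondary objective in every part. The figure most often quoted from a safety table is its any-event row, and that row would add symptomatic or fatal progression to all other events.

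At stake is how the tolerability figures read: how many patients died with a TEAE, had a Grade 3+ TEAE or stopped because of one, and how soon. If progression is to be set apart, the terms should be chosen before the results are seen.

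**Working it through.** There is no sample size, power or alpha figure to reproduce. The check is mainly one of tracing events through the text, with one arithmetic illustration.

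**Step 1: which progression events reach which outputs** (given onset in the TEAE window)

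| Event | AE? | Serious? | Outputs reached |
|---|---|---|---|
| Scan-only progression | No (protocol 10.1) | No | None |
| Symptomatic, not fatal | Yes (10.1) | No (10.4) | Grade 3+ if so graded; discontinuation table and all-cause time-to-first if that action is recorded |
| Fatal in the safety reporting period | Yes, Grade 5 (10.4) | Yes | Grade 3+, serious and fatal; discontinuation and time-to-first on the same condition |

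The discontinuation route depends on how sites code the event. Protocol section 10.7 requires an action taken for each AE, section 10.7.3 offers permanent discontinuation as one choice, and section 12.1 makes progression a reason to stop (section 7.4.4 allows agreed exceptions). Nothing says whether a symptomatic-progression AE should carry that action. The route is open, but its size is unknown.

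**Step 2: what the planned outputs already separate**

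- Preferred-term rows show events coded as progression. The any-event row does not exclude them.
- Separate treatment-related tables exist for all TEAEs and serious TEAEs. None is listed for Grade 3+, fatal or discontinuation. A missing relationship counts as related.
- The disposition table gives the primary reason for stopping, but no rule reconciles it with the discontinuation TEAE table.
- No summary of deaths by cause is planned. Overall survival (SAP section 12.2.3) covers Part 2B only and counts death from any cause.

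**Step 3: why subtracting the progression row is not enough**

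Let A be the patients with any event in a table, B those in the progression row, and C those with progression and at least one other event.

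Total without progression = A − B + C.

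C is not reported, so a reader knows only that the total lies between A − B and A. In the fatal table C should be small, and subtraction may nearly work. In the Grade 3+ table patients can have several events, so it does not. The 1-KM curve has no term rows, so nothing can be subtracted from it.

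**Step 4: illustration for the fatal table**

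Inputs, both from protocol section 3.2.2.1: 163 patients in the November 2014 safety cut, and five deaths, for which "all deaths were due to disease progression and were assessed as not related to rucaparib". Limits are exact (Clopper-Pearson).

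- Progression counted: 5/163 = 0.0307, or 3.1%. The lower limit is the 2.5th percentile of Beta(5, 159) = 0.0100, and the upper limit is the 97.5th percentile of Beta(6, 158) = 0.0701. The interval is 1.0% to 7.0%.
- Progression set apart: 0/163 = 0%. The upper limit is 1 − 0.025^(1/163) = 0.0224. The interval is 0 to 2.2%.

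This assumes that all five deaths belong to the 163 patients and fall in the TEAE window. Each death that does not lowers the first figure by 1/163 = 0.6 percentage points, so it ranges from 0 to 3.1%.

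**The case against.** The strongest reply is that a TEAE is defined by timing, so listing an event does not attribute it to rucaparib. Attribution is carried by the relationship summary and the treatment-related outputs. In an open-label trial without a control, keeping every event whatever its judged cause is a defensible, conservative default. Fatal progression has a named recording term, so it should appear on its own line. Non-fatal progression, and hospitalization for it, are kept out of the serious table at source. Scan-only progression never becomes an AE, and the disposition table gives the reason for stopping. In section 3.2.2.1 the sponsor already describes deaths by cause and relationship.

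Most of this stands, and it sets the limits of the point. The planned all-TEAE tables are legitimate and should stay. The serious table is affected only by fatal progression. The treatment-related time-to-first analysis is not in question.

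It does not supply the missing totals. Term rows cannot be subtracted where patients have several events, the all-cause curve cannot be decomposed, and the fatal, Grade 3+ and discontinuation tables have no listed treatment-related version. The sponsor's own statements in section 3.2.2.1, on deaths by cause and on the absence of treatment-related discontinuations, correspond to no table listed in SAP section 14.1.

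The remedy has a limit too: symptoms of progression coded under their own terms would remain in every total.

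**Conclusion.** The point holds as a gap in the planned totals. Progression enters the AE data by protocol rule, and SAP section 14.1 has no rule for it in the any-event totals of the Grade 3+, fatal and discontinuation tables, in the serious table (fatal progression only), or in the all-cause time-to-first analysis. Existing outputs reduce the mixing only in part.

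The size can be illustrated for deaths alone: 3.1% (1.0 to 7.0) against 0% (0 to 2.2). That rests on the two assumptions stated with the calculation. The 163 patients are pooled from ongoing Phase 2 studies, the deaths are counted to 30 days and not 28, and SAP section 4 rules out pooling across parts. The figures show direction and are not a forecast for this trial. No figure in the documents sizes the effect on the other tables or on the curve.

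A reader might infer more, and the documents do not support it:

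- That the fatal and discontinuation rates would mostly measure the cancer, or that the discontinuation table is distorted at least as much as the fatal one. No data are given, and scan-only progression is excluded.
- That the tables do not separate progression at all. They do so by preferred term.
- That the safety objective cannot be met. Its endpoint is the incidence of AEs and of laboratory and ECG abnormalities, and the planned tables deliver it.

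No primary efficacy analysis or decision rule is affected. This is a cheap improvement that would change reported tolerability figures.

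**What to change.** In SAP section 14.1:

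1. Pre-specify a list of preferred terms for progression of the cancer under study.
2. Keep the planned all-TEAE tables. Add to the Grade 3+, serious, fatal and discontinuation tables a total that excludes those terms.
3. Add a version of the all-cause time-to-first analysis without those terms, and state how patients with no other qualifying event are censored. Leave the treatment-related version as it is.
4. Summarize on-study deaths as progression versus other cause.

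The cost is a term list and a few reruns of planned outputs, with no new data. The SAP already groups preferred terms, so the programming is familiar. A footnote should say that progression symptoms coded under their own terms are not removed.

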## 14.2 Clinical Laboratory Evaluations

Clinical laboratory evaluations include the continuous variables for hematology, serum chemistry, and urinalysis. The laboratory values will be presented in SI units. The on-treatment period will be defined as the time from initiation of study drug to 28 days after the last dose of study drug. Laboratory values collected during the on-treatment period will be included in the summary tables. The laboratory values collected after the on-treatment period will only be presented in the data listings.

The summary of laboratory data will include descriptive statistics (N, mean, SD, minimum, median, and maximum) of the maximum, minimum and last value during the on-treatment period. Summaries using descriptive statistics of the change from baseline to the maximum, minimum, and last value during the on-treatment period will also be given.

Shift summary tables from baseline to the maximum on-treatment toxicity grade (CTCAE Version 4.03 or higher) for each lab parameter will be summarized.

Laboratory data including normal ranges and abnormal laboratory flags will be provided using by-patient listings.

### 14.3 Vital Signs

The on-treatment period will be defined as the time from initiation of study drug to 28 days after the last dose of study drug. Vital sign measurements collected during the on-treatment period will be included in the summary tables. The vital sign measurements collected after the on-treatment period will only be presented in the data listings.

The summary of vital sign data will include descriptive statistics (N, mean, SD, minimum, median, third quartile and maximum) of the maximum, minimum and last value during the on-treatment period. Summaries using descriptive statistics (N, mean, SD, minimum, median and maximum) of the change from baseline to the maximum, minimum, and last value during the on-treatment period will also be given. The data will be presented separately for each randomized treatment group and overall.

### 14.4 Electrocardiograms (ECG)

Electrocardiogram (ECG) was analyzed intensively for Part 1 and reported separately in an ECG report. For the other study parts (Part 2A, 2B and Part 3) local reads of ECG was collected at each visit. The QT interval was corrected by using both Fridericia's (QTcF) and Bazett's (QTcB) formula. The QTcF and QTcB intervals will be stratified into categories indicative of potential clinical significance. Each patient's maximum QTc intervals from the pretreatment visit and treatment period visits will be classified as  $\leq 450$  msec,  $>450$  to  $\leq 480$  msec,  $>480$  to  $\leq 500$  msec, and  $>500$  msec. For each patient's maximum change from the pretreatment ECG visit for QT and QTc, intervals will be classified into  $<30$  msec,  $\geq 30$  to  $<60$  msec, and  $\geq 60$  msec. Patients will also be classified according to the CTCAE grade 3 criteria of at least 2 on treatment QTc values  $>500$  ms. The number and percentage of patients in each classified category will be presented.

Descriptive statistics will be used to summarize other ECG parameters of PR, QRS, QT, and RR interval, and the corresponding changes from pretreatment ECG visit at each time point.

